3.2 Schedule of assessments (SoA)

Table 1 - Schedule of follow-up Assessments

	COVID-19 (2 weeks ¹ ± 2 weeks)	3 months ¹ ± 1 month	6 months ¹ ± 1 month	12 months ¹ ± 1 month	18 months ¹ ± 2 months
Screening/baseline					
Inclusion criteria ¹					
Demographics ²					
Healthcare setting ³					
Length of hospital stay, days					
ICU admission					
Medical history ⁴					
Treatment					
Comorbidity management ⁵	Х	Х	Х	Х	Х
Anti-COVID therapy ⁶	Х				
Antibiotic therapy ⁷					

Oxygen therapy ⁸	v	X*	X*	X*	X*				
SARS-CoV-2 vaccination ⁹	X X	X	X	X	X				
Clinical assessment	Λ	Λ	Λ	Λ	Λ				
Relevant medical new events ¹⁰	Х	Х	X	Х	Х				
COVID-19 symptom ¹¹ onset	X	Λ	Λ	Λ	Λ				
		V*	V*	V*	V*				
COVID-19 symptom end	X	X*	X*	X*	X*				
COVID severity ¹²	X X								
SOFA score		37	37	37	37				
Vital signs ¹³	X	X	X	X	X				
Physical examination ¹⁴	Х	X	X	X	X				
12-lead electrocardiography	X	X	X	X	X				
6-minute walking test	Х	Х	Х	Х	Х				
DLCO (diffusing capacity for car- bon monoxide)	Х	Х	Х	Х	Х				
Pulmonary function test ¹⁵	Х	Х	X	Х	X				
Questionnaires									
Functional status ¹⁶	Х	Х	Х	Х	Х				
Respiratory impairment ¹⁷	Х	Х	X	Х	Х				
Mental health ¹⁸	Х	Х	X	X	Х				
Perceived risk of re-infection/ad-									
mission/re-admission ¹⁹	Х	Х	Х	Х	Х				
Adherence to main preventative	Х	Х	Х	Х	Х				
non-pharmacological measures ²⁰	Λ	А	А	А	Λ				
SARS-CoV-2 vaccination: ac-									
ceptance/non-acceptance and rea-	Х	Х	Х	Х	Х				
sons ²¹									
Imaging									
Lung ultrasound	Х	X	X*	Х	X*				
X-ray	Х	Х	X*	X*	X*				
High-resolution CT scan	Х	Х	X*	X*	X*				
Cardiac ultrasound	Х	Х	X*	Х	X*				
Cardiac MRI ²²	X^{21}	X^{21}	X*	X^{21}	X*				
Biochemistry									
Blood tests ²³	Х	X	X*	Х	X*				
Arterial blood gas test	Х	х	X*	X*	X*				
(pO ₂ /pCO ₂ /pH)									
Urine tests ²⁴	Х	X	X*	Х	X*				
Immunology			1						
Immune - serology and type I IFNs autoantibodies	Х	Х	X	Х	Х				
Immune - cytokine and chemokine	Х	X ³⁵	X 35	X ³⁵	X *				
Immune - cellular	X	X 35	X 35	X 35	X *				
Microbiological tests-NP swabs	11								
Viral variant and metagenomics									
sequencing	Х	X*,34	X*,34	X*,34	X*				
EDTA whole blood									
Genetic and epigenetic analysis	Х	X	X	Х	Х				
Stool Sample (faeces or rectal									
swab)									
Metagenomic sequencing	Х		Х		Х				
	unctive variable	s for specific fr		ns					
HIV									
HIV-infection status ²⁵	Х	Х	X	X	Х				
HIV-Infection therapy 26	X	X	X	X	X				
Assessment of adherence to fol-	4 8								
low-up visits and antiretroviral	Х	Х	X	Х	Х				
therapy	-		_	-	-				

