1.2		1	1	ı					

Elderly					
Cognitive status ²⁷	Х	Х	Х	Х	Х
Pregnant women/new mother					
History of positive SARS-CoV-2					
molecular test on amniotic fluid or					
breast milk ²⁸					
History of detection of micro-					
thrombotic disease on placenta tis-					
sue or umbelical cord tissue					
Children					
History of positive SARS-CoV-2					
molecular test on amniotic fluid or					
breast milk ²⁸					
Biometric paramethers ²⁹	Х	Х	Х	X	Х
Transplant					
Transplant general information ³⁰					
Graft function ³¹	Х	Х	Х	Х	Х
Immunosuppressive regimen ³²	Х	Х	Х	Х	Х
Onco-haematology					
Assessment of adherence to onco-	Х	х	X	х	х
logic follow-up visits and therapy	Λ	Λ	Λ	Λ	Λ
Assessment of progression of the	Х	X	x	х	х
disease and relapse	Λ	Λ	Λ	Λ	Λ
Assessment of adverse events ³³	Х	Х	Х	Х	Х

Footnotes

Modular data capture according to level of commitment (level I, level II, level III).

Level I	Assessments in level I are mandatory
Level II	Customized according to the feasibility of each cohort

- * Reassessed only if outside the normal ranges at the previous assessment or if clinically indicated
- 1. Day 0: first positive SARS-CoV-2 test
- Demographics: age (years), sex, ethnic group (African, Asian, European, Latin America...), education (no formal education, lower than college, college or higher), cigarette smoking (never-smoker, former smoker, current smoker), usual residence (home, long-term care facility, public dormitory, prison, homeless), current occupation (student, unemployed with no benefits, unemployed with benefits, employed, self-employed, informal worker)
- 3. Healthcare setting: (a) outpatient (b) non-intensive care unit (c) intensive care unit.
- 4. Medical history: cardiovascular diseases (hypertension, coronary artery disease, congestive heart failure), diabetes (without insulin, with insulin), chronic respiratory disease (asthma, chronic ob-

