10. INCLUSION AND EXCLUSION CRITERIA

Inclusion criteria:

- Any age
- Any comorbidity
- Laboratory confirmed SARS-CoV-2 infection by PCR diagnosis from nasopharynx, oropharynx, bronchoalveolar lavage, stool, or blood. Rapid tests are an acceptable alternative.
- Person (or attorney or deputy who has been authorized to make the decision for patients who lack capacity) consent to participate.

Exclusion criteria:

• Refusal to participate to the study.

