12. STUDY PROCEDURES

The assessments of this study are designed to improve the COVID-19 patient care in the context of routine clinical care. Considering the lack of standardized follow-up pathways for COVID-19 patients, the selection of assessments has been based on available evidence and according to the definition of good clinical practice.

The organization of follow-up visits will be up to each center, according to the facilities and logistics of outpatient monitoring.

There will be a modular data capture according to the level of commitment of each cohort.

- Level I: Assessments in level I are mandatory
- Level II: Customized according to the feasibility of each cohort

The modular schedule of assessments is presented in Table 1. Overall, the follow-up will last 18 months. Day 0 corresponds to the time of the first positive SARS-CoV-2 test. The screening/baseline data collection (including the informed consent process, as detailed in section 14.3) can be carried out on the same day of a follow-up visit (as detailed in section 11). Procedures conducted as part of the participant's routine clinical management at the time of SARS-CoV-2 active infection and obtained before the signature of the informed consent form may be recorded, provided that the procedures meet the protocol-specified criteria.

Subsequent follow-up visits will occur at the following time-points: 3, 6, 2, 18 month(s). During each time-point, epidemiological data collection (SARS-CoV-2 vaccination status), treatment data collection (comorbidity management), clinical assessments (relevant medical new events, COVID-19 symptom assessment, physical examination, vital signs, 6-minute walking test), and the administration of questionnaires on functional status, respiratory impairment, and mental health will be performed as part of level I (mandatory) assessments, as well as the assessment of the SARS-CoV-2 immunological status (SARS-CoV-2 antibodies). A SARS-CoV-2 molecular test will be repeated only if it turned out positive at the previous follow-up visit.

Self-administered questionnaires on symptoms, as listed in Table 1, will be completed daily by the participant to provide timely data on the symptom length. The participant will assign a score based on symptom severity, which will be recorded daily in the self-administered diary: absent (0), mild (1), moderate (2) and severe (3).

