As detailed in Table 1, level II (imaging, biochemistry, pulmonary function tests, electrocardiography) will be performed according to the capability of each cohort and will be based on the clinical evaluation, according to the participant's healthcare status. Imaging and biochemistry tests will be reassessed only if outside the normal ranges at the previous follow-up visit or if clinically indicated. During the follow-up visit at month 12, cardiac and lung ultrasounds, blood and urine tests will be offered as part of the participant's care.

COVID-19 biological samples (including blood, naso-pharingeal swabs, urine, and stool) will be collected and stored in the biobank of each participating center (according to local ethic commission recommendations). The Azienda Ospedaliera Integrata Universitaria (AOUI) of Verona developed a COVID-19-VR registry for biobanking COVID-19 biological samples to allow further research and national/international collaborations. As per protocol approved by the hospital Institutional Review Board (IRB 2577CESC), biological samples of COVID-19 patients are stored in the LURM (Laborato-

rio Universitario di Ricerca Medica). Test to be performed in a centralised laboratory (genomic, transcriptomic, cytokine, viral analyses, PBMCs and genetic and epigenetic see Table 2) will be sent, following international regulation, to the University of Antwerp, INSERM, University of Bologna or HMGU. A dedicated protocol will be developed for expeditions procedures. Nasal swabs collected prospectively for diagnosis of SARS COVID-2 will be collected in the local laboratory and sent out to University of Antwerpen and INSERM. Stool simple for microbiological analysis will be sent out to University of Bologna (see Table 2). Whole blood samples for epigenetic and genetic analysis will be sent out to UNIBO, INSERM and Helmholtz Zentrum Munchen (HMGU). In-depth human genetic analysis will be conducted using WGS or whole exome sequencing (WES) followed by functional analyses of the most promising variants. Genome-wide methylation analyses of COVID-19-positive patients in addition to a small number of control patients will enable differentiation of inherited and acquired genomic regulatory features through COVID-19 infection, which result in severe disease or an efficient clearing of infection through immune responses.

Table 2 - Samples collected at SARS-CoV-2 diagnosis and at follow up.

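### Section 12 says methylation analysis will separate inherited from acquired features, but patients have no pre-infection sample and the controls are undefined, so the design as described does not support the claim

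*Combined protocol and SAP*

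**What the plan says.** The claim is in Section 12 (Study procedures). Genome-wide methylation is to be measured in COVID-19-positive patients "in addition to a small number of control patients", and this "will enable differentiation of inherited and acquired genomic regulatory features through COVID-19 infection". The sentence then attributes severe disease, or efficient clearance of the infection, to the features found. The sentence before it plans whole-genome or whole-exome sequencing.

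The sampling times are in Table 1 (Section 3.2). The row "Genetic and epigenetic analysis" is marked at all five time points, the first headed "COVID-19 (2 weeks ¹ ± 2 weeks" and the others at 3, 6, 12 and 18 months. Footnote 1 sets the clock: "Day 0: first positive SARS-CoV-2 test". Section 12 repeats this, and Table 2 is titled "Samples collected at SARS-CoV-2 diagnosis and at follow up".

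Eligibility (Section 10) requires "Laboratory confirmed SARS-CoV-2 infection by PCR diagnosis from nasopharynx, oropharynx, bronchoalveolar lavage, stool, or blood", with rapid tests accepted as an alternative. Section 11 lets a patient enter at any point up to the end of the 18-month follow-up if at least one visit can be made.

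Section 5 says that the wider ORCHESTRA project includes SARS-CoV-2-negative people, but nothing links them to the methylation controls. Section 13 describes no analysis of methylation data.

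**The concern.** To say that a methylation feature was inherited or acquired through infection, one needs to know its state before infection, or to have a comparison that stands in for that state. The schedule gives no patient such a sample, and the comparison group is mentioned without being described.

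The direction of effect is at stake. The sentence presents the features as leading to severe disease. In Table 1, severity and anti-COVID therapy are recorded in the same acute column as the first epigenetic sample. A methylation difference that goes with severity could therefore precede severe illness, accompany it, or follow from it or its treatment. If the sentence stands as the rationale for the analysis, a consequence of severe infection could be reported as its pre-existing cause.

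**Working it through.** The plan gives no sample size, effect size or error rate for the methylation analysis. The 10000 in Section 13 is expected enrolment for the whole study. There is no figure to reproduce, so the check is on what the scheduled samples can identify.

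**Step 1: timing in patients (Table 1, footnote 1).** The windows after day 0 are:
- acute: 2 − 2 = 0 to 2 + 2 = 4 weeks
- month 3: 3 ± 1, so 2 to 4 months
- month 6: 6 ± 1, so 5 to 7 months
- month 12: 12 ± 1, so 11 to 13 months
- month 18: 18 ± 2, so 16 to 20 months

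Day 0 is a positive test, so infection is already present at the lower limit of the first window. Pre-infection time points: 0 of 5.

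**Step 2: late entry (Section 11).** The 0-to-4-week window describes patients who are sampled in the acute phase. A patient recruited at a later visit may have a first study sample many months after infection.

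**Step 3: what the samples identify.** For one methylation site, let B be the level before infection and A(t) the change caused by infection at time t.
- A patient sampled at t gives B + A(t).
- Two samples from one patient give A(t2) − A(t1), and B cancels. For any constant c, replacing B by B + c and every A(t) by A(t) − c leaves all the data unchanged. Serial samples show change after infection, but a persistent infection effect looks the same as a pre-existing level.
- Patients minus uninfected controls gives (mean B in patients − mean B in controls) + mean A(t). This is one equation with two unknowns. It yields mean A(t) only if the two groups had the same mean B before infection, which these samples cannot test.

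**Step 4: what sequencing adds.** Write B = G + E, where G is methylation tied to inherited DNA sequence and E is other pre-existing methylation (age, smoking, comorbidity). Inherited sequence does not depend on when blood is drawn, so sequencing can help identify G. It does not separate E from a persistent A.

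**Step 5: the controls.** Step 3 needs controls who are uninfected and comparable. Section 12 gives no number, infection status, source, matching or sampling time, and Section 10 has no entry route for an uninfected person.

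**Step 6: what a within-patient analysis would have to work with.** Acute-to-month-12 change uses blood that is already scheduled, with these limits:
- Late entrants may lack the acute sample.
- Follow-up ends in June 2023. The month-12 window opens at 11 months, so infections after about July 2022 (June 2023 less 11 months) will not reach it.
- Blood counts are scheduled at month 12. At month 18 they are repeated only if previously abnormal or clinically indicated, so month 12 is the better endpoint. Biochemistry is level II, so some cohorts may lack counts at either visit.
- Only survivors who stay in follow-up contribute.

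**The case against.** The strongest defence is that the protocol does not rely on patient samples alone. It adds controls, plans sequencing in the preceding sentence, and samples patients at five points. Inherited versus acquired is also not the same contrast as pre-existing versus consequence: smoking-related methylation is pre-existing but not inherited, and germline sequence can speak to inheritance whenever blood is drawn. The governing objective is worded modestly, as markers indicative of severity; the Section 8 version names only sequencing and functional analysis. The disputed text is one sentence in a procedures section.

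Much of this stands, and it rules out three stronger readings. A reader might infer that every sample in the analysis is post-infection. That is shown for infected patients only; the controls may be uninfected, and the documents do not say. A reader might infer that the separation is impossible. Steps 3 and 4 show that comparable uninfected controls, serial samples and sequence data could give partial evidence under assumptions. A reader might infer that the first sample always falls within four weeks of the first positive test. Section 11 contradicts that.

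The defence does not rescue the unqualified wording. The elements that could help are undefined (the controls), not linked to this analysis in Section 13 (sequencing), or silent on persistent effects (serial samples). The synopsis does name epigenetic analysis as a means to the severity-marker objective, so the sentence is not idle.

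**Conclusion.** The claim is stronger than the design. No infected patient has a scheduled pre-infection sample (0 of 5 time points), late entrants may first be sampled many months after infection, and the control group is undefined. The protocol therefore does not show how inherited and acquired features would be told apart, nor does it support the implication that the features found cause severe disease.

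The conclusion rests on the schedule and eligibility as written. It would soften if the controls proved to be uninfected and comparable, or if patient samples banked before infection existed; the documents mention neither. Even then, pre-existing non-inherited methylation and blood-cell composition would remain rival explanations unless handled in the analysis.

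The size is small: one sentence, supporting the last-listed secondary objective. No primary objective depends on it.

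**What to change.** - **Restate the aim** in Section 12 as the association of post-infection methylation with severity, and change in methylation over time after infection. Remove the statement that the analysis will separate inherited from acquired features, and the implication of cause.
- **Define the controls.** Give their number, source and sampling times, and state that they are uninfected and matched at least on age, sex and smoking. Otherwise drop the inherited/acquired contrast.
- **Use the planned sequencing** to identify sequence-linked methylation, and say so in Section 13.
- **Add a within-patient analysis**, not necessarily as the main one: change from the acute to the month-12 sample among patients who have an acute sample, adjusted for blood-cell composition (measured lymphocyte and neutrophil counts where available). Report how many patients contribute and that they are retained survivors.
- **Label** differences that persist unchanged as not distinguishable from pre-existing.

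The cost is a weaker claim and a little more analysis. No new patient samples are needed, because the epigenetic blood is already scheduled. Matched uninfected controls may take some effort to secure; dropping the contrast avoids that.

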13. STATISTICAL ANALYSIS

Sample size calculation. The number of inclusions will depend on the progress of the SARS-CoV-2 pandemic, which is unknown at this time. Therefore, the number of patients who will be included cannot be determined in advance. However, depending on the timing of the project and the included cohorts, the expected enrollment is 10000 subjects.

We will carry out comprehensive descriptive analyses taking into account sociodemographic factors and clinical courses. The frequency distributions of the characteristics will be given in absolute and relative numbers, median plus interquartile range (IQR) or mean values plus 95% confidence interval (CIs). Associations with specific treatment strategies, disease severity patterns and laboratory results will be analysed using chi-square tests, t-tests or Mann-Whitney tests, depending on the data. To evaluate potential risk factors, multivariate regression models will be carried out. Outcome time analyses using Cox proportional-hazards regression models with time-dependent covariates will be performed to examine

factors associated with each endpoint (including death). In addition, we will use cumulative incidence functions, such as the Fine-Gray subdistribution hazard regression model, to account for competing events (i.e., relocation, discharge against medical advice, etc.). For missing values, a different strategy to understand the causes and the significance for the analysis will be developed and a graduated procedure for dealing with censorship and imputations via linked regressions will be developed. The significance level is defined with a p-value <0.05. All statistical analyses will be carried out with STATA, Python and/or R statistics software by trained staff (epidemiologists, statisticians) using the latest analysis methods.

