9.1. University of Verona (UNIVR) – Italy

UNIVR will participate to the recruitment of COVID-19 general population and COVID-19 fragile populations: HIV positive, solid organ transplanted, oncological (both solid cancer and haematological neoplasms) patients and elderly people resident in LTCFs (General nursing home; residential home; specialized LTCFs; mixed LTCFs, other LTCFs; overall number of beds; ownership of the facility: public, for profit, not for profit). Estimated number of COVID-19 patients since the beginning of the pandemic: 66000

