9.4. COVID-HOME study

University Medical Center Groningen (UMCG), Groningen, Netherlands

Prospective cohort study of non-hospitalised COVID-19 patients. The COVID-HOME study focuses on the community and household with early, systematic and prospective long-term follow-up The parameters collected in this study, such as viral load, antibody response, cyto-kine changes and clinical and laboratory parameters of patient evolution will allow the identification of independent factors/parameters determining evolution of disease, insight in other transmission routes than respiratory ones (such as sexual and faecal-oral), and immune response dynamics in non-hospitalised patients.

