9.6. ZIKAction

Led by Penta, the ZIKAction research consortium brings together 14 partners across South and Central America, the Caribbean and Europe with the complementary goals of 1) developing a multidisciplinary multinational ready to-act network capable of rapidly addressing any maternal and paediatric research need arising from (re-)emerging infectious diseases including Zika virus and 2) conducting an interdisciplinary programme of research studies within this network to address key knowledge gaps relating to ZIKV epidemiology, natural history and pathogenesis, with a particular emphasis on maternal and child health. ZIKAction is funded by the European Union's Horizon 2020 Programme. ZIKAction works closely with two other European Union-funded consortia, ZikaPLAN and ZIKAlliance, to establish a Latin American and Caribbean network. Within this research consortium, the SARS-oV-2 sub-study will address issues related to COVID-19 infection in pregnant women and children.

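### Section 13 gives no method for correlation within care facilities or households, and the data described hold no link to identify them; results for factors shared within a cluster may be too optimistic

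*Combined protocol and SAP*

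**What the plan says.** Section 13 gives the analysis in one paragraph. Associations with treatment strategy, severity pattern and laboratory results "will be analysed using chi-square tests, t-tests or Mann-Whitney tests, depending on the data". For risk factors, "To evaluate potential risk factors, multivariate regression models will be carried out". Cox models with time-dependent covariates and Fine-Gray models follow. On error control there is one sentence: "The significance level is defined with a p-value <0.05". Clustering, robust variance, generalised estimating equations, random effects, frailty and stratification by facility, household or centre are not mentioned anywhere in the document.

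Two cohort descriptions point to patients who live together. Section 9.1 lists among the Verona populations "elderly people resident in LTCFs", with facility type, bed count and ownership as descriptors. Section 9.4 says "The COVID-HOME study focuses on the community and household with early, systematic and prospective long-term follow-up". A third source is only possible: the ZIKAction sub-study in section 9.6 "will address issues related to COVID-19 infection in pregnant women and children", without saying that they enter as pairs.

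The data described cannot link such patients. The demographics footnote to Table 1 records the kind of residence, not which one. The patient code in section 14.5 holds a centre part and a person part, and the same section leaves identity with the enrolling centre alone.

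**The concern.** Residents of one facility, or members of one household infected in the same outbreak, are likely to share the variant, the calendar period and much of their care. Their sequelae, antibodies and microbiome are then likely to be correlated. The two-sample tests, and the default standard errors of the regression models, treat each patient as independent information. For a factor that is the same for everyone in a cluster, the effective sample is smaller than the head count and the nominal 5% level is not kept. Variant is such a factor, and it appears in the second and third main objectives in section 8.

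The first main objective is descriptive. A positive correlation makes naive intervals for rates and means in these sub-cohorts too narrow, whatever the exposure.

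The missing link matters as much as the missing sentence. A model can carry a cluster term only if the cluster is recorded, and on the data described a central analyst could not reconstruct it without going back to the centres.

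**Working it through.** **The plan's own figure.** Section 13 says that "the number of patients who will be included cannot be determined in advance" and then that "the expected enrollment is 10000 subjects". No power, precision or design effect lies behind this number, so there is nothing to reproduce.

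**Inputs.** Alpha is 0.05 (section 13; two-sided is assumed, as the sidedness is not stated). Not in the document, and therefore assumed: patients per cluster *m*, the intraclass correlation ICC, and the share of analysed patients who are clustered.

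**Formulas.**
- Factor constant within a cluster: DEFF = 1 + (m − 1) × ICC.
- Factor balanced within clusters: DEFF ≈ 1 − ICC.
- Clustered patients only a share *s* of the analysis set: average DEFF = 1 + s × (m − 1) × ICC.
- True type I error of a nominal 5% test: 2 × [1 − Φ(1.96/√DEFF)]. With DEFF = 1 this returns 0.050.
- The correct interval is √DEFF times as wide as the naive one.

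**Every analysed patient clustered, factor constant within the cluster.**

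| Cluster | ICC | DEFF | True type I error | Interval ratio |
|---|---|---|---|---|
| Pair, m = 2 | 0.10 | 1 + 1 × 0.10 = 1.10 | 0.062 | 1.05 |
| Pair, m = 2 | 0.30 | 1 + 1 × 0.30 = 1.30 | 0.086 | 1.14 |
| Household, m = 3 | 0.10 | 1 + 2 × 0.10 = 1.20 | 0.074 | 1.10 |
| Household, m = 3 | 0.30 | 1 + 2 × 0.30 = 1.60 | 0.121 | 1.26 |
| Facility, m = 20 | 0.05 | 1 + 19 × 0.05 = 1.95 | 0.160 | 1.40 |
| Facility, m = 20 | 0.10 | 1 + 19 × 0.10 = 2.90 | 0.250 | 1.70 |

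**Pooled analysis with only a share clustered, same kind of factor.**

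| Share | Pairs, ICC 0.10 to 0.30 | Facilities of 20, ICC 0.05 to 0.10 |
|---|---|---|
| 5% | 0.051 to 0.052 | 0.056 to 0.061 |
| 10% | 0.051 to 0.054 | 0.061 to 0.072 |
| 20% | 0.052 to 0.057 | 0.072 to 0.095 |
| 50% | 0.056 to 0.068 | 0.107 to 0.161 |

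For example, 10% in facilities with ICC 0.10 gives 1 + 0.1 × 19 × 0.10 = 1.19, hence 0.072.

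**Factor balanced within clusters.** DEFF is 0.90 to 0.70 for ICC 0.1 to 0.3, and the true error is 0.039 to 0.019, which is conservative.

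**Check by simulation.** The uncorrected chi-square test was run on beta-binomial clusters: 800 patients, 4,000 runs, outcome rate 0.35. That rate is borrowed from the survey in section 5 as an illustration; it is not a planning value.

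| Setting | Factor constant in cluster | Factor unrelated to cluster | Factor balanced in cluster |
|---|---|---|---|
| Pairs, ICC 0.2 | 0.076 | 0.050 | 0.035 |
| Pairs, ICC 0.3 | 0.093 | 0.051 | 0.022 |
| Facilities of 20, ICC 0.05 | 0.170 | 0.052 | 0.042 |
| Facilities of 20, ICC 0.10 | 0.252 | 0.049 | 0.046 |

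The simulation agrees with the formula for cluster-constant factors and confirms that there is no inflation for the others.

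**The case against.** Much can be said for the plan. Section 11 describes recruitment of individuals by hospitals, clinics and primary care networks, not sampling of clusters. Section 10 requires confirmed infection, so uninfected household members do not enter, and section 9.4 does not say how many members per household do. Facility residents are one group within one cohort, with no numbers given. The sentence on two-sample tests concerns treatment, severity and laboratory results, which mostly vary between people in the same facility or household; for those the error stays at or below about 5%. The eCRF itself is not in the document, so a link field can be called undescribed but not absent. The plan also names no single confirmatory test whose error rate would be compromised.

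All of this limits the point, and four stronger readings fall with it:
- A reader might infer that section 13 prescribes independent-patient standard errors throughout. It is silent on variance, and the regression, Cox and Fine-Gray models can all carry a cluster term.
- A reader might infer that patients are recruited as clusters. Here clustering arises from shared residence.
- A reader might infer that mothers and children are enrolled as pairs. Table 1 asks about a positive test on amniotic fluid or breast milk in both modules, which fits pairing, but paired enrolment is not stated.
- A reader might infer that every p-value is too small. The direction depends on whether the factor varies between or within clusters.

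What remains is that facility residents and a household-focused cohort are in the study, that variant is a main-objective factor likely to be shared within an outbreak, and that neither a method nor a link is described.

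**Conclusion.** The point stands in a limited form and is worth acting on. For factors shared within a facility or household, and for descriptive rates and means in those sub-cohorts, the plan as written may give p-values and intervals that are too optimistic. In an analysis made up only of facility residents (20 per facility, ICC 0.05 to 0.10), the true type I error for a cluster-constant factor would be about 16 to 25%, and intervals should be 1.4 to 1.7 times as wide. For pairs with ICC 0.1 to 0.3 the error is about 6 to 9%.

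It would be tempting to carry the upper figures over to the whole study. The document does not support that, because they require every analysed patient to be in a cluster. If 10% are, the pooled error is about 6 to 7% for facilities and about 5% for pairs. Cluster size, ICC and clustered share are all assumptions, and the averaging treats clustered patients as spread evenly over the groups compared. The larger figures therefore belong to sub-cohort analyses, which section 9 foresees.

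**What to change.** In the eCRF, add a pseudonymous facility or household link ID, and a mother-child link where pairs are enrolled. The centre can assign it, so no identity needs to leave the centre.

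In section 13, state that association analyses including these sub-cohorts use cluster-robust variance, or a random intercept (frailty for the Cox model), on that ID in place of the plain two-sample tests. The Fine-Gray model can use clustered variance. Intervals for rates and means in these sub-cohorts should use the same ID. Specify a small-sample correction when facilities are few, because sandwich errors are unreliable there.

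Include recruiting centre as a stratum or random effect. It is already in the patient code and concerns far more patients: LEOSS alone has more than 2,500 patients over 250 sites, about 10 per site. A centre term does not replace the link ID, since it leaves correlation within a facility or household untouched.

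The cost is somewhat wider intervals and one added field. Centres must also back-fill the ID for patients already enrolled or entered retrospectively, which is real work because only they hold the identities.
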